Variability in cognitive performance within and across assessments is common in both healthy and neurologically-impaired populations and may exceed two standard deviations in some cases. Practice effects are also common and generally attributable to increased familiarity with test materials, content, and process. To help mitigate these potential influences on test scores, Reliable Change Indices (RCI) [26] will be calculated at the 3 and 12 month reassessments. RCI's are determined by first subtracting the mean T2 - T1 change from the difference between the two testings for each individual, and then comparing it to 1.64 times the standard deviation of the difference. A difference of this magnitude is exceeded only 10% of the time (in either the positive or negative direction) if there is no real change. Applying a correction to change scores is particularly important in samples that include patients with severe TBI, as practice effects are magnified at higher levels of impairment and with shorter test-retest intervals [27].

All subjects will also undergo a neurophysiologic examination at the time of their baseline cognitive testing, and at 6 weeks, 12 weeks, 24 weeks and 52 weeks.

To control for the potential confounding effects of mood, pain and subjective distress on treatment, we will administer self-report measures in these areas at the time of enrollment. Scores on the Beck Depression Inventory, modified Brief Pain Inventory and British Columbia Post-Concussion Scale, obtained at baseline, will be used as covariates in our primary analysis. We will also use time post-injury as a covariate to control for the possible influence of length of time since injury on treatment outcome as spontaneous recovery will be more rapid in subjects enrolled early versus late, and because those enrolled later will be higher functioning at baseline.

Screening/Follow-up measures:

- Galveston Orientation Amnesia Test (GOAT): A series of 10 questions asked to a patient to help evaluate posttraumatic amnesia. The test is repeated at each visit, and is scored on a scale of 0 to 100. A patient is determined to be out of the amnesic state when the score exceeds 75 on three consecutive examinations.

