The anticipated loss to follow-up rate in this study is around 15% - like our other drug studies. To account for this loss-to-follow-up rate, a total of 15 patients per group (30 total) will be enrolled in the study. The primary analysis will be an intent-to-treat analysis that will include all randomized participants regardless of their compliance with the study treatment or follow-up schedule. Study subjects should have received at least 1 dose of study drug/placebo. All hypothesis testing will be conducted using $\alpha = 0.05$, two-sided.

To analyze the data, we will compare means using t-test and modeling the data with ANOVA for multivariate analysis controlling for baseline values and other important covariates. If necessary, non-parametric approaches including Mann-Whitney and Friedman's test for multivariate analysis will be used with data that are not normally distributed. We will also use Fisher's exact test for comparison of categorical variables such as proportion of adverse effects. In summary, we will use the following statistical tests according to our primary aims:

• Primary Aim: To determine whether Huperzine A, as compared with placebo, has a differential effect on learning and memory functions after moderate to severe TBI.

For this aim we will compare means using t-test (comparing differences (Week 12 – baseline) between the two groups) and modeling the data with ANOVA for multivariate analysis controlling for baseline values and other important covariates (for secondary analysis). If necessary, non-parametric approaches including Mann-Whitney and Friedman's test for multivariate analysis will be used with data that are not normally distributed.

• Secondary aim 1: To determine whether administration of Huperzine A produces significant differences in neurophysiologic markers (as indexed by EEG event related potentials (P50 and P300) and TMS-indexed cortical excitability (cholinergic activity)) associated with cognition, relative to a placebo.

For this aim we will also build models in which the main dependent outcome will be amplitude or latency measures (from P50, P300 and SAI) and the independent variables will be group, time and the interaction group*time.

• Secondary aim 2: To determine whether Huperzine A reduces the prevalence of post-traumatic seizures after moderate and severe TBI as compared to placebo

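### The intent-to-treat primary analysis cannot include subjects with no Week 12 CVLT-II, and no missing-data method is given for them

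*Combined protocol and SAP*

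**What the plan says.** Section X (Statistical Analysis) describes the primary analysis as an "intent-to-treat analysis that will include all randomized participants regardless of their compliance with the study treatment or follow-up schedule". The next sentence narrows this: "Study subjects should have received at least 1 dose of study drug/placebo". For the primary aim it names a t-test "comparing differences (Week 12 – baseline) between the two groups". Rank-based tests are a fallback for non-normal data. An ANOVA is added, "controlling for baseline values and other important covariates (for secondary analysis"), whereas Section IX says the baseline mood, pain and symptom scores "will be used as covariates in our primary analysis".

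On loss, Section X anticipates about 15% and responds by enrolling more: "To account for this loss-to-follow-up rate, a total of 15 patients per group (30 total) will be enrolled in the study". Section IX has all outcome measures taken in person. The telephone fallback in Section VIII (Follow-up Assessments) covers symptoms, adverse events and medication changes, not the CVLT-II.

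Section VIII (transition procedures) says follow-up will be attempted whether or not dosing was completed. It treats anyone who returns for no follow-up assessment as lost. A subject who cannot return within the one-week deferral is to be analysed as non-compliant, a term that is not defined. Section XII (Dropout in the placebo group) expects placebo subjects may stop treatment more often, and relies on the intent-to-treat population as the safeguard.

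**The concern.** An intent-to-treat label fixes who should be analysed. It does not supply an outcome for someone who was not measured. A change score needs both values, so a subject with no Week 12 CVLT-II drops out of the primary test unless a rule brings that subject in, and the plan has none.

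Enrolling extra subjects restores power but does not remove bias if those who are lost differ from those who stay. The trial's stated purpose is to supply effect sizes and variances for the next trial, so a shift in the estimate would carry into that trial's sample size.

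**Working it through.** **The plan's own figures.** Section X gives group changes of 4.67 (SD 4.51) and 0.33 (SD 2.50). The root-mean-square SD is √[(4.51² + 2.50²)/2] = 3.65, and 4.34/3.65 = 1.19, as stated. A two-sample t-test at 80% power and two-sided 5% needs 12.12 per group, so 13 per group and 26 in all, as stated. Then 26 × 1.15 = 29.9, which gives the 30 enrolled. The test is therefore sized on about 26 subjects with data, not on the 30 randomized.

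**Can any named analysis use a subject with no Week 12 score?**
- t-test or Mann-Whitney on change: no, the change does not exist.
- Friedman's test: no, it needs complete blocks.
- ANOVA of Week 12 adjusted for baseline and covariates, whether called primary or secondary: no, the outcome is missing.
- Group-by-time models: specified only for P50, P300 and SAI.

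**Expected number.** 30 × 0.85 = 25.5 with data if the whole 15% falls by Week 12. The plan does not date this loss, and follow-up runs to Week 52.

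**Power is not the issue.** At an effect of 1.19, power is 0.88 with 15/15, 0.83 with 13/13 and 0.82 with 15/11.

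**Size of bias (dropout assumed).** If k of 15 placebo subjects are missing and average D SD worse than placebo completers, the completer estimate shifts by -(k/15) × D.
- k = 2: -0.07 (D = 0.5) to -0.13 (D = 1.0).
- k = 4: -0.13 to -0.27, which is 11% to 22% of 1.19.
- In points for k = 4: 0.33 to 0.67 at SD 2.50, or 0.60 to 1.20 at SD 4.51. Groups A and B are not identified, so either SD could be the placebo one.
- Standard error in SD units: √(1/15 + 1/15) = 0.365 with no loss; √(1/15 + 1/11) = 0.397 with 4 lost.
- With k = 4 and no true effect, two-sided rejection is 6% to 10%, but rejections favouring Huperzine A are about 1% or less, against a nominal 2.5%.
- Planning the next trial at 1.19 less the shift multiplies its sample size by (1.19/1.057)² = 1.27 to (1.19/0.923)² = 1.66.

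**What a model could recover.** Simulation with 15 per arm, no true effect, equal SDs and all correlations 0.6 (assumed), 15,000 trials per row, Monte Carlo error about 0.003. The worst 4 placebo subjects are lost and none from active, which is deliberately adverse. Shifts are in SD of change.

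| Loss follows | Change-score t-test | Baseline-adjusted completers | Repeated-measures model |
|---|---|---|---|
| Week 6 change | -0.21 | -0.13 | 0.00 |
| Week 12 change, Week 6 seen | -0.42 | -0.35 | -0.31 |
| Week 12 change, no follow-up score | -0.42 | -0.35 | -0.35 |

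With no loss, the standard error falls from 0.364 (t-test) to 0.332 for both the baseline-adjusted comparison and the model, so that gain is entirely baseline adjustment. In the second row, 0.07 of the 0.11 improvement is baseline adjustment. In the third row all of it is. Only in the first row does the Week 6 score contribute more (0.13 of 0.21).

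**The case against.** The inclusion promise can be read as keeping off-schedule or non-adherent subjects, and Section XII speaks of stopping treatment, which intent-to-treat does address. That much stands: a subject who stops drug but is tested at Week 12 is properly retained, and Section VIII supports that follow-up. It does not help a subject who is not tested.

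Loss by Week 12 may also be smaller than 15%. Subjects are contacted two weeks before each visit and have a window of two weeks either side. Those at high risk of non-compliance are not randomized, and the Week 12 visit is paid at $100 with travel reimbursed. These measures reduce the problem but do not give an analysis rule.

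The strongest objection is to a model-based remedy. For subjects the plan defines as lost to follow-up there is no Week 6 score, and the repeated-measures estimate equals the baseline-adjusted completer comparison that Section X already lists. The documents do not show that loss would follow the Week 6 score, the pattern in which the model does best. This stands, and it limits what can be claimed for the model.

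A reader might infer that the plan risks a false claim of benefit. The only uneven pattern it foresees is in placebo, and loss of poor performers there works against Huperzine A. The mirror-image loss of 4 active subjects would put false rejections favouring the drug at about 5% to just under 10%. However, nothing in the documents predicts it, and Section XII expects no significant adverse effects leading to non-adherence on active drug.

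**Conclusion.** The inconsistency is real: the plan promises all randomized subjects and specifies tests that can use only those with a Week 12 score. The claimed protection against uneven dropout holds for treatment discontinuation with assessment retained, and not otherwise.

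The likely size is modest. In the illustration the shift is -0.13 to -0.27 SD, inside one standard error. The deliberately adverse simulations reach about -0.42, slightly above it. All rest on assumed dropout patterns, because the documents give no Week 12 missingness by arm. If loss is unrelated to outcome, only power falls.

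It should not be inferred that 25 or 26 analysed is a forecast, that the trial becomes underpowered at its own planning effect, or that the intent-to-treat safeguard is worthless. The exploratory label lowers the stakes, but an estimate meant for sizing the next trial should come with a stated missing-data assumption. This should be changed, at small cost.

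**What to change.** 1. Make the primary Week 12 comparison baseline-adjusted, through a likelihood-based repeated-measures model of the Week 6 and Week 12 CVLT-II with treatment-by-visit terms, a small-sample degrees-of-freedom correction and subjects analysed as randomized. Keep the change-score t-test as supportive, since the trial was sized on it.
2. State the missing-at-random assumption. Say plainly that much of the gain is baseline adjustment, that the Week 6 score helps only subjects who have one and mainly when loss follows it, and that the model adds nothing beyond baseline-adjusted completers for subjects with no follow-up score.
3. For those subjects, and for loss that depends on the unseen Week 12 score, add one delta (tipping-point) sensitivity analysis over all randomized subjects, in both directions, increasing the shift until the conclusion changes.
4. Report by arm how many lack a Week 12 score and how many have no follow-up score.
5. Reconcile the wording: all randomized against the one-dose condition; covariates in the primary analysis (Section IX) against the secondary label (Section X); and a statement that being analysed as non-compliant does not remove a subject from the primary set. Limit the Section XII claim to subjects who stop treatment but are still assessed.

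Cost: no new data, because the Week 6 CVLT-II is already scheduled; slightly more analysis; and reliance on a stated assumption. The primary test would also change after the by-group look that followed the first 10 subjects, so it should be a dated amendment made while still blinded to treatment identity.

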- 3. Outpatients will be referred from other healthcare facilities, the community, or the treating physician.

Once referred, study staff will approach subjects who retain decision-making capacity, or the authorized representative of a patient who lacks decision-making capacity, for permission to complete a screening for possible enrollment. Please note that clearance for consent will follow standard clinical procedures. A co-investigator/coordinator will review with the potential subject/authorized representative the informed consent form, and clearly explain all the procedures and risks of the testing. The subject/authorized representative will be encouraged to ask questions, both during the initial interview and throughout the study. The PI or a co-investigator/coordinator will answer any questions regarding the study during the consent process. During the enrollment interview, the subject/authorized representative will be instructed not to take any prescribed or over-the-counter herbal supplements or nutraceuticals during participation in this study to avoid potentially confounding study results. Once enrolled, the subject may terminate his/her participation at any time during the study.

VIII. STUDY PROCEDURES

Study Design:

This is a randomized, double-blind, placebo-controlled phase II study. We plan to enroll 30 subjects with moderate to severe TBI (Huperzine = 15, Placebo = 15). Subjects may be inpatients or outpatients. Subjects will receive study drug or placebo for 12 weeks, and follow-up will continue through Week 52. Subjects enrolled in this study will receive standard acute and rehabilitative care. All subjects will be enrolled at Spaulding. Spaulding inpatient subjects who are discharged from Spaulding prior to closure of the active treatment window (at week 12) will continue to be followed either by telephone or in-person. Weekly phone calls between the study coordinators and subjects (or their authorized representative) will ensure that, for each subject actively enrolled, the dosage of study medication is correct, any new adverse events (including seizure) have been captured and any concerns raised by the subject or study staff have been addressed.

Recruitment and Consent

SRH Inpatients

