 - c. If the subject returns to the study within 1 week, he/she will continue the dosage schedule at the last administered dose. If the subject is unable to return within 1 week, he/she will be analyzed as a non-compliant patient.

IX. DESCRIPTION OF ASSESSMENT AND OUTCOME MEASURES

Outcome measures:

The outcome measures, assessment schedule, and change indices we selected are designed to optimize capture of the primary treatment effect (CVLT-II) while considering normal variation in test performance as well as practice effects which may occur with repeated assessments. The proposed test battery consists of measures selected from the NIH NCMRR TBI study group for the COBRIT study [23].

All outcome measures will be assessed in person, with the following schedule: baseline (pretreatment), 6, 12, 24, and 52 weeks post-intervention.

The primary outcome measure, the California Verbal Learning Test-II (CVLT-II), is sensitive to attention, memory and aspects of executive functions, all of which may be altered by Huperzine A because of their dependence on dopaminergic and cholinergic activity. The CVLT-II will be administered at baseline, 6 weeks, 12 weeks, and 52 weeks. With the exception of the 24-week timepoint, these assessment points coincide with the neurophysiologic assessment schedule

(described below) and will allow us to explore the correspondence between temporal changes in biologic and cognitive markers associated with the intervention.

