Because effects will be dependent on patients taking Huperzine, treatment compliance will be essential in our study. We will measure compliance by asking the subject and/or caretaker to return the medication bottles at the end of the titration and maintenance periods. Any remaining pills will be counted, returned to the pharmacy and documented in the subject's folder, with specific forms. If the subject is still inpatient, we will monitor compliance through the medication administration system. Finally, we do not expect significant adverse effects associated with the use of Huperzine that would lead patients receiving this drug to become non-adherent.

Dropout in the placebo group:

Participants in the placebo group may disproportionately discontinue the study treatment since there will be little or no improvements in cognitive function. Although, this fact could bias the results, we expect that the placebo group will also have a small improvement (due to natural recovery, though smaller than in the active group) and we will conduct an analysis of the data using an intent-to treat population, to protect against disproportionate dropout.

XIII. POTENTIAL BENEFITS

It is possible that subjects participating in this research may benefit from the Huperzine-A given in the trial. Additionally, subjects may benefit from the use of TMS as the data could suggest plasticity changes and encourage clinicians to continue therapy or other interventions. Lastly

subjects may benefit from the close follow-up and enhanced observation of the clinical research team.

XIV. STIPEND

Each subject will receive a total of \$450 paid throughout their study participation. The stipend payment distribution is as follows: Screening \$25, Baseline \$25, Week 6 \$50, Week 12 \$100, Week 13 \$50, Week 24 \$100 and Week 52 \$100.

In addition, travel, parking and/or hotel costs will be reimbursed up to \$200/ subject. Proof of payment of costs will be required for reimbursement.

Plan for Future Studies:

A major goal of this study is to collect data that may be useful to plan future phase II/III trials. In fact, this is one of the major goals of phase II studies that usually test several outcomes as there are no strong data to support a large trial. Therefore, with this study we expect to:

- (1) Determine parameters for sample size calculation such as effect sizes for different endpoints.

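### Friedman's test, apparently the non-parametric stand-in for the covariate-adjusted analysis, has no term for treatment arm and should be replaced in that role

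*Combined protocol and SAP*

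**What the plan says.** Section X describes the analysis twice, once in general and once under the Primary Aim, with the same structure. The parametric methods are a t-test, which under the Primary Aim compares Week 12 minus baseline differences between arms, and "modeling the data with ANOVA for multivariate analysis controlling for baseline values and other important covariates (for secondary analysis"). The words in that bracket, which make the adjusted model secondary, appear only under the Primary Aim. Section IX instead places the baseline depression, pain and post-concussion scores in the primary analysis and adds time since injury as a further covariate.

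For non-normal data both paragraphs say "If necessary, non-parametric approaches including Mann-Whitney and Friedman", and the sentence goes on: "test for multivariate analysis will be used with data that are not normally distributed". No other rank method is named for the adjusted analysis, and no criterion is given for when the fallback applies.

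The aim being tested is comparative: "To determine whether Huperzine A, as compared with placebo, has a differential effect on learning and memory functions after moderate to severe TBI". The design is two separate randomized groups: "We plan to enroll 30 subjects with moderate to severe TBI (Huperzine = 15, Placebo = 15"). No matching is described. Outcomes are repeated within subject: "All outcome measures will be assessed in person, with the following schedule: baseline (pretreatment), 6, 12, 24, and 52 weeks post-intervention".

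**The concern.** Friedman's test ranks the repeated measurements inside each subject and asks whether some occasions tend to rank higher than others. Here the only within-subject factor is visit. Randomized arm does not enter the statistic, and neither baseline nor any covariate can be added.

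The protocol expects scores to change without any drug effect. Section IX warns of practice effects and spontaneous recovery. Section XII, on dropout in the placebo group, says "we expect that the placebo group will also have a small improvement". Friedman's test picks up exactly that shared change. If its p-value were reported where the adjusted treatment comparison belongs, it would answer a question about time, not about Huperzine A. The trial is meant to supply effect sizes for later studies, and such a result would carry no treatment information.

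**Working it through.** **Which method replaces which.** Set side by side, the two lists in Section X are:
- parametric: t-test; ANOVA for the multivariate analysis;
- non-parametric: Mann-Whitney; Friedman for the multivariate analysis.

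Mann-Whitney matches the t-test, which leaves Friedman matching the adjusted ANOVA. This is read from the wording; the plan does not state it outright.

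**The plan's sample size, used as the simulation size.** Section X gives changes of 4.67 (SD 4.51) and 0.33 (SD 2.50) in two groups labelled A and B.
- Pooled SD with equal weights: sqrt((4.51² + 2.50²)/2) = sqrt(13.295) = 3.65.
- Effect size: (4.67 − 0.33)/3.65 = 1.19, as stated.
- Two-sided alpha 0.05 and 80% power (stated for the original calculation, assumed for this one), noncentral t: 12.12, so 13 per group and 26 in total, as stated.

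**Arm is absent from the statistic.** Friedman's Q = 12/(nk(k+1)) × ΣRⱼ² − 3n(k+1), where Rⱼ is the rank sum of visit j over all n subjects and k is the number of visits. Arm appears nowhere. In a simulated data set, reshuffling which subjects belong to which arm left Q at 2.385.

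**Rejection rate with no drug effect, in SD units.** Assumptions: 26 subjects with complete data; normal scores; equal within-subject correlation of 0.6 to 0.7; visits at baseline, Week 6 and Week 12; the same mean change in both arms, with 70% of it reached by Week 6.

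| Shared change by Week 12 | Friedman significant at 5% |
|---|---|
| 0 | about 5% |
| 0.2 SD | 12–15% |
| 0.35 SD | 30–39% |
| 0.5 SD | 57–70% |

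At 0.5 SD, Mann-Whitney on change rejects in 4.4–4.5% and Quade's rank ANCOVA in 4.4–4.9%.

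**The same check in score points.** This version uses the SD of change of 3.65, 26 subjects, and half of the change reached by Week 6.

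| Shared change (points) | Friedman significant at 5% |
|---|---|
| 0 | 4.6% |
| 0.33 (group B's mean) | 5.9% |
| 1.0 | 15.8% |
| 1.78 (weighted interim mean) | 43.2% |
| 3.0 | 86.9% |

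The weighted mean is (3 × 4.67 + 6 × 0.33)/9 = 1.78, taking the stated 3:6 ratio in the order A:B. At 1.78 the rate runs from 28.9% (SD 4.51) to 76.4% (SD 2.50). Over all settings tried, with 26 or 30 subjects, the t-test on change rejects in 4.6–5.5% and Mann-Whitney in 3.7–5.2%.

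**The two scales compared.** With correlation r, the SD of change is sqrt(2(1 − r)) score SDs: 0.894 at 0.6 and 0.775 at 0.7. A shift of 0.5 SD is therefore 0.5/0.894 = 0.56 to 0.5/0.775 = 0.65 change SDs, or about 2.0 to 2.4 points at 3.65.

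**The opposite failure.** Take a true arm difference of 4.34 points and no net change over time (one arm up 2.17, the other down 2.17). Friedman rejects in 3.2%, the t-test in 82.2% and Mann-Whitney in 78.6%. The case is artificial, but it shows that the test can also miss a real treatment effect.

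**The case against.** The strongest reply is that little hangs on this sentence. The main comparison for the primary aim is the t-test on change, and its rank counterpart, Mann-Whitney, stands in the same sentence and is valid. The adjusted model is labelled secondary in Section X, the fallback is conditional, and the study calls itself exploratory. With outcomes at several visits, Friedman's test might have been meant only as a loose description of change over time; nothing says its p-value would be reported as a treatment effect. The shared change may also be small: Section XII expects only a small placebo improvement, and at 0.33 points the inflation is slight (5.4–8.4% across the SDs and sample sizes tried).

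Most of this stands, and it limits the point. A reader might infer that the primary result itself is compromised. The documents do not support that, because Mann-Whitney on change protects it; the doubt that remains comes from Section IX placing the covariates in the primary analysis. A reader might also infer that the fallback will probably be used. The documents give no distributional data and no normality criterion, so its use is possible but cannot be called likely. Nor does the plan propose running Friedman's test within each arm and contrasting the two p-values, so the error rate of that practice should not be charged to it.

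What does not stand is the descriptive reading as a full answer. No text limits Friedman's test to that role, and if that is all it does, the adjusted analysis has no non-parametric fallback.

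**Conclusion.** The point holds as a correction to a conditional fallback. On the most natural reading, Section X replaces an analysis that compares arms and adjusts for covariates with a test that does neither. That is so whatever the size of the shared change.

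The numerical consequence is uncertain. With no drug effect, the chance of a significant Friedman result runs from about 5% with no shared change to 57–70% at 0.5 SD. No single figure in that range can be defended from the documents, because they do not give the shared change or the within-subject correlation. The groups in the interim look are not identified by arm, so 0.33 and 4.67 only mark out a range. The simulations also assume normal, complete data.

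The unadjusted primary comparison and its Mann-Whitney fallback are unaffected. The weight of the defect depends on whether the adjusted model is secondary (Section X) or primary (Section IX). It should be corrected, but it does not undermine the trial.

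**What to change.** In Section X, in both the general paragraph and the Primary Aim paragraph, replace Friedman's test as the fallback for the adjusted analysis with a method that contains arm. Either of these would do:

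- a rank-based ANCOVA (Quade): regress the ranked Week 12 score on ranked baseline and the same covariates as the parametric model (depression, pain and post-concussion scores, time since injury), then compare the residuals between arms;
- a permutation test of the arm term in the ANCOVA.

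The choice between them is a matter of preference, but one should be named in advance. Keep Mann-Whitney on the Week 12 minus baseline change as the unadjusted fallback, and say that it replaces the t-test. If Friedman's test stays, limit it to describing change over time and state that it is not evidence of a treatment effect. Sections IX and X should also agree on whether the adjusted model is primary or secondary.

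The cost is SAP wording. Standard software suffices, and no new data, visits or subjects are needed.
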